7.3.3 Safety analyses

Major bleeding events will be analysed as a secondary endpoint. All bleeding events and combined endpoint of major and clinical-relevant bleeding events will be analysed by the Cox proportional hazards model with treatment being the factor and stratified by age group if appropriate. Pooling of age groups or non-stratified analysis might be performed if the event rate is low. All safety analyses as well as all bleeding events and all-cause mortality analysed as efficacy endpoints will be performed on the treated set.

The safety analysis set will include all randomized patients who take at least one dose of study medication. Patients in the safety population will be analysed according to the study treatment they have received. The safety analyses will be descriptive in nature and will be based on BI standards. The safety analyses will include the following parameters:

- All AEs
- protocol-specified AESI
- serious AEs
- AEs leading to treatment discontinuation

AEs will be coded using the MedDRA dictionary. All AEs will be classified according to the following trial periods: screening, on-treatment, post treatment. All AEs with an onset date/time after the 1st dose of trial medication up to 6 days after the last intake of study medication will be assigned to the treatment period for evaluation. In addition, AEs with onset date before start of the trial treatment but with worsening in intensity during the treatment will also be assigned to the on-treatment period. Other AEs will be assigned to the screening or post-treatment period, respectively. All AEs (including bleeding) in the treatment period will be tabulated in total and according to seriousness, severity and possible relationship to trial medication. AEs in the screening or follow-up period will be listed.

Other lab data, vital signs, physical examinations data and ECG data will be reported descriptively.

Proprietary confidential information.

© 2019 Boehringer Ingelheim International GmbH or one or more of its affiliated companies. All rights reserved.

This document may not - in full or in part - be passed on, reproduced, published or otherwise used without prior written permission.

Proprietary confidential information.

© 2019 Boehringer Ingelheim International GmbH or one or more of its affiliated companies. All rights reserved.

This document may not - in full or in part - be passed on, reproduced, published or otherwise used without prior written permission.

7.3.5 Pharmacokinetic analyses

The analysis of the PK/PD parameters will be performed on PKS.

All concentrations will be listed and summarized descriptively. The concentrations will be compared descriptively with the exposure observed in adult patients or healthy subjects previously.

PK data from this study along with data from other trials in the dabigatran program will be used to further refine the adult population pharmacokinetic model, allowing it to be used for the generation of predictions optimized for paediatric populations. The results of this model refinement will be reported separately.

7.3.6 Pharmacodynamic analyses

The following descriptive statistics will be calculated for the pharmacodynamic parameters aPTT, ECT and any additional PD assay: these include, but are not limited to N, arithmetic mean, standard deviation, minimum, median, and maximum. Further, ratios to baseline (i.e. visit 2) for these parameters will be calculated and assessed by descriptive statistics.

7.3.7 Pharmacogenomic analyses

Not applicable.

7.4 HANDLING OF MISSING DATA

Missing data will not be imputed in general. For complete thrombus resolution assessment, if the assessment at Visit 8 (84 days) is missing, then the last observation at eEOT visit will be carried forward providing there is no VTE related events occurred between the two visits. All patients will be followed to collect necessary efficacy and safety information, even if patients discontinue study medication prematurely.

7.5 RANDOMISATION

Interactive response technology (IRT) will be used to randomize patients to treatment groups. The randomization will be performed in blocks and stratified by age groups, and the allocation ratio will be 2:1 for dabigatran to SOC. The randomization list will be generated using a validated system, which involves a pseudo-random number generator to guarantee the reproducibility of the assignments. In addition, patients assigned to dabigatran OLF will be

Proprietary confidential information.

© 2019 Boehringer Ingelheim International GmbH or one or more of its affiliated companies. All rights reserved.

This document may not - in full or in part - be passed on, reproduced, published or otherwise used without prior written permission.

randomized based on 1:1 ratio to receive flavoured or unflavoured solvent for reconstitution. This randomization list will be checked by an independent statistician and will be used by a third-party IRT to assign randomization numbers to eligible patients.

7.6 DETERMINATION OF SAMPLE SIZE

After an extensive literature search, 11 articles which were relevant to thrombus resolution in paediatric patients with VTE ([R07-2937](#), [P16-07690](#), [P08-12132](#), [P11-06995](#), [P14-05231](#), [R16-2873](#), [R16-2876](#), [R16-2877](#), [R16-2878](#), [R16-2879](#), [P16-03657](#)) were included in a meta-analysis of the complete thrombus resolution rate using SOC anticoagulants (predominantly low-molecular weight heparins or vitamin K antagonists) after a careful screening. Most of the studies are not randomized controlled clinical trials. However, a Bayesian meta-analysis concluded a stable mean complete thrombus resolution rate of 72% using data from the 11 studies. This rate was used as the assumption which both dabigatran etexilate and SOC would have achieved in this trial.

A complete thrombus resolution rate without treatment cannot be established from recent publications. It is uncommon to see patient completely without treatment, and the rate of complete thrombus resolution is believed to be low. This is specifically true for cases not involving a central line, such as DVT/PE, which will represent the majority of case in this trial. Central line thrombosis, which has a potentially better resolution rate due to catheter removal, is predominantly expected to occur in younger children (below the age of approximately 2 years). However, the number patients in stratum 3 is approximately 15 only, therefore, the number of central line thrombosis in this trial is expected to be low overall. Thus, the clot resolution rate under no treatment in this trial is predominantly resulting from the DVT/ PE cases included.

In the absence of solid evidence of spontaneous thrombus resolution, a precise effect size is difficult to be determined. As an alternative, a wide range of plausible complete thrombus resolution rate without treatment (5% to 20%) have been considered, and it has been demonstrated that the proposed 20% non-inferiority margin can preserve at least 62% and up to 70% of the effect size under SOC treatment.

Table 7.6: 1 Effect size preserved by 20% NI margin

Complete thrombus resolution rate of SOC (based on meta-analysis result)	72%			
Complete thrombus resolution rate without treatment (plausible assumptions)	5%	10%	15%	20%
Effect size preserved by 20% NI margin	70%	68%	65%	62%

With a total sample size of 141 patients and a 2:1 randomization to dabigatran and SOC, respectively, approximately 94 patients will be randomized to receive dabigatran and approximately 47 patients to receive SOC. The following simulation has been performed to consider the variability in the estimate of the complete thrombus resolution rate. Assuming the number of complete thrombus resolution follows binomial distribution with unknown probability of success, the estimates of the complete thrombus resolution rate are subject to the variability of this distribution. One hundred thousand binomial samples were generated

Proprietary confidential information.

© 2019 Boehringer Ingelheim International GmbH or one or more of its affiliated companies. All rights reserved.

This document may not - in full or in part - be passed on, reproduced, published or otherwise used without prior written permission.

for dabigatran arm and SOC arm, with 94 and 47 patients respectively. The lower bound of the 90% confidence interval was calculated for each simulation using:

$$\hat{p}_{dabi} - \hat{p}_{soc} - 1.64 \times \sqrt{\frac{\hat{p}_{dabi}(1 - \hat{p}_{dabi})}{94} + \frac{\hat{p}_{soc}(1 - \hat{p}_{soc})}{47}}$$

where, \hat{p}_{dabi} and \hat{p}_{soc} are point estimates of the complete thrombus resolution rates of dabigatran arm and stand of care arm from each simulation. Samples are generated from binomial distribution assuming the true complete thrombus resolution rates are p_{dabi} and p_{soc} , respectively. The proportions of the lower bound above the non-inferiority margin among the 100,000 simulations are provided in the table below, under various assumptions of binomial distributions.

Table 7.6: 2 Summary of power estimates for primary efficacy endpoint with a sample size of 141

Assumptions used in generating simulated samples	Power of 90% CI lower bound above the non-inferiority margin -20%
Superior assumption: $(p_{dabi}, p_{soc}) = (0.77, 0.72)$	95%
Non-inferior assumption: $(p_{dabi}, p_{soc}) = (0.72, 0.72)$	82%
Suboptimal assumption: $(p_{dabi}, p_{soc}) = (0.68, 0.72)$	63%
Extremely conservative but non-inferior assumption: $(p_{dabi}, p_{soc}) = (0.62, 0.72)$	33%
Inferior assumption: $(p_{dabi}, p_{soc}) = (0.52, 0.72)$	5% (false positive)

Under the assumption that the true unknown complete thrombus resolution rate is 72% of both dabigatran and SOC, the proposed sample size of 141 is sufficient to demonstrate non-inferiority with adequate power (82%).

If the complete thrombus resolution rate in dabigatran is truly lower than the SOC, the chance of showing non-inferiority drops to 33% when the difference is 10% (complete thrombus resolution rate 62% vs 72% for dabigatran and SOC, respectively), and to below 5% when the non-inferiority margin of 20% is reached (complete thrombus resolution rate 52% vs 72% for dabigatran and SOC, respectively).

However, the most likely scenario for the paediatric population is to assume similar thrombus resolution rates with both dabigatran and SOC, based on the following considerations: primary efficacy results obtained from adult VTE RE-COVER-trials ([P13-16985](#)) demonstrated robust non-inferiority. In addition, it is the expectation that the gMean trough concentration in the paediatric trials will exceed the average trough exposure of RE-COVER due to the option of up-titration of the dose if initial exposure is < 50 ng/ml compared to fixed dosing in the adult trials. Therefore the Sponsor considers the sample size and 20% margin are reasonably sensitive to evaluate non-inferiority in the paediatric population. See Table 7.6: 3 for summary.

Proprietary confidential information.

© 2019 Boehringer Ingelheim International GmbH or one or more of its affiliated companies. All rights reserved.

This document may not - in full or in part - be passed on, reproduced, published or otherwise used without prior written permission.

Table 7.6: 3 Summary of power estimates for the primary endpoint with a sample size of 141

One-sided confidence level	Primary endpoints (non-event rate)	True rate difference	Margin for rate difference	Power [#]
90%	72%	0.0%	20%	82%
95%	72%	0.0%	20%	71%

[#] Power for the non-inferiority approach is computed as the proportion of 100,000 simulations in which the observed upper bound of one-sided confidence intervals for $p_{1C} - p_{1D}$ and $p_{2C} - p_{2D}$ (assuming 94 and 47 evaluable patients in dabigatran arm and control arm, respectively) are below the specified equivalence margin. The confidence interval for the VTE endpoint is estimated by Newcombe-Wilson method ([R08-4386](#)).

A discontinuation rate of up to 15% before the completion of at least 3 months treatment with dabigatran has been estimated for both 1160.106 and 1160.108 trials. 94 patients will be randomized to receive dabigatran in 1160.106 trial. It is estimated that there will be 120 patients entering 1160.108 by end of recruitment. Assuming that 20% of 1160.106 dabigatran patients will be rolled over to 1160.108, this would result in roughly 101 of the 120 total patients receiving dabigatran treatment in 1160.108 trial to be unique patients. Across both trials, this would result in $94 + 101 = 195$ unique patients treated with dabigatran. With a discontinuation rate of 15% (i.e. stop of treatment earlier than 3 months), a total of 166 unique patients are expected to complete at least 3 months of dabigatran treatment in both trials together.

Proprietary confidential information.

© 2019 Boehringer Ingelheim International GmbH or one or more of its affiliated companies. All rights reserved.

This document may not - in full or in part - be passed on, reproduced, published or otherwise used without prior written permission.

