
Proprietary confidential information.

© 2019 Boehringer Ingelheim International GmbH or one or more of its affiliated companies. All rights reserved.

This document may not - in full or in part - be passed on, reproduced, published or otherwise used without prior written permission.

Name of company: Boehringer Ingelheim		Tabulated Trial Protocol	
Name of finished product: Not applicable			
Name of active ingredient: Dabigatran etexilate, BIBR 1048 MS			
Protocol date: 05 June 2013	Trial number: 1160.106		Revision date: 06 Feb 2019
Criteria for safety: 
 • Incidence of bleeding events including: 
 ○ Major bleeding events, clinically relevant non-major (CRNM) bleeding events, minor bleeding events and any bleeding events ○ Combined endpoint of major and CRNM bleeding events • Incidence of adverse events, protocol-specified AESIs and serious adverse events • Treatment discontinuation due to an adverse event • Change from baseline in safety laboratory values, vital signs and physical examination • Global assessment of tolerability (measured as treatment discontinuation and adherence) to study medication 			
Statistical methods: The primary efficacy endpoint will be tested for non-inferiority using non-inferiority margin of 20% at one-sided level of 0.05. Upon showing non-inferiority for the primary endpoint, superiority test for the primary endpoint will be performed subsequently at one-sided level of 0.05 without multiplicity correction. Mantel-Haenszel type weighted average of proportion difference, Kaplan-Meier method, Cox proportional hazard model, Logistic regression and descriptive statistics will be used in the planned analyses.			

Proprietary confidential information.

© 2019 Boehringer Ingelheim International GmbH or one or more of its affiliated companies. All rights reserved.

This document may not - in full or in part - be passed on, reproduced, published or otherwise used without prior written permission.

FLOW CHART

Trial Period	Screening	Treatment Period (open-label) with Dabigatran Etexilate (Dabi) or Standard Of Care (SOC)											Follow-up ^A	
		1 ^X	2	3 ^B	4	5 ^Y	6	7	8 ^C	Dabi Titration ^B Visit if needed ^B	INR/anti-Xa Visit if needed ^B	Unscheduled Visit if needed ^D		eEOT ^E Only for early discontinued patients (before Y8)
Visit (V) #:	1 ^X	2	3 ^B	4	5 ^Y	6	7	8 ^C						
Study week	-2	1	1	2	3	6	9	12						V8 or eEOT + 28 days

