An open-label multicentre randomized study (the REVIVE study) comparing the efficacy and safety of a low molecular weight heparin (reviparin-sodium) to UFH/VKA for the treatment of VTE in children, showed that at 3 months post-therapy, 2/36 patients (5.6%) treated with reviparin-sodium had recurrent VTE or death compared to 4/40 patients (10.0%) receiving UFH/VKA (odds ratio = 0.53; 95% CI=(0.05, 4.00); Fisher's exact test: 2P= 0.677). There were 7 major bleeds reported, 2/36 (5.6%) in the reviparin-sodium group and 5/40 (12.5%) in UFH/VKA group (odds ratio = 0.41; 95% confidence interval 0.04, 2.76); Fisher's exact test: P=0.435). There were 5 deaths reported during the study period, 1 (2.8%) in the reviparin-sodium group and 4 (10.0%) in the UFH/VKA group. All five deaths were considered unrelated to VTE but one was due to an intracranial haemorrhage in the UFH/VKA group. Due to slow patient accrual, REVIVE was closed prematurely. The REVIVE study provides

Proprietary confidential information.

© 2019 Boehringer Ingelheim International GmbH or one or more of its affiliated companies. All rights reserved.

This document may not - in full or in part - be passed on, reproduced, published or otherwise used without prior written permission.

valuable information on the incidence of recurrent VTE, major bleeding and problematic issues associated with therapy of VTE in children ([R06-2304](#)).

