7.4 PRIMARY ENDPOINTS

Primary analysis

The primary analysis of the primary efficacy endpoint will be performed on the randomized set following the intention-to-treat (ITT) principle, based on adjudicated data. For example: patients who were originally randomized to DE and later switched to SOC before Day 84, as cases of premature termination of the study medication, will be further followed up per the visit schedule until Day 84.

The analysis period in the primary analysis starts from the time of randomization to the time point of interest, that is, Day 84 \pm 7 days.

- For patients who die or withdraw consent prior to Day 84 – 7 days, the period for the primary analysis ends with the date of trial completion (i.e. the date of death, or the date of consent withdrawal).
- For patients who discontinue treatment prematurely (for example, due to complete thrombus resolution, AE, DE concentration out of target range after one dose modification, and so on), the latest available thrombus assessment up to Day 84 + 7 days will be used for the primary analysis. In particular, thrombus assessment performed after eEOT but before/at Visit 8 for patients switching from DE to SOC will be used for primary analysis. In terms of the recurrent VTE component or VTE-related mortality component, recurrence or death up to Day 84 + 7 days will be used for primary analysis.
- Patients who are still being treated and have not yet reached Day 84 \pm 7 days at time of EMA interim data cut-off will not be included in the analysis

The primary efficacy endpoint contains three components. Given the composite nature of the primary endpoint, each component will be evaluated separately, and a joint outcome of achieving the primary endpoint will be concluded only if all three components are satisfied.

Component 1: free from VTE-related mortality

Patients with VTE-related death occurring between randomization to Day 84 + 7 days will be considered as NOT meeting the endpoint in terms of the component of “freedom from mortality related to VTE”, and therefore will not contribute to the proportion of patients achieving the primary efficacy endpoint.

Component 2: free from recurrent VTE

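### Protocol 7.6 labels 82% as power for the three-part primary endpoint, but computes it from complete thrombus resolution alone; the cited paediatric data put it at about 77-82%

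*Protocol*

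**What the plan says.** The synopsis sets the test: "The primary efficacy endpoint will be tested for non-inferiority using non-inferiority margin of 20% at one-sided level of 0.05". Protocol 7.2 and 5.1.1 define the endpoint as complete thrombus resolution together with freedom from recurrent VTE and from VTE-related death. SAP 7.4 scores it the same way: "a joint outcome of achieving the primary endpoint will be concluded only if all three components are satisfied".

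Protocol 7.6 derives its planning rate from resolution only: "a Bayesian meta-analysis concluded a stable mean complete thrombus resolution rate of 72% using data from the 11 studies". It continues: "This rate was used as the assumption which both dabigatran etexilate and SOC would have achieved in this trial". With 2:1 allocation, "approximately 94 patients will be randomized to receive dabigatran and approximately 47 patients to receive SOC". The simulation then draws binomial counts of complete thrombus resolution, forms a 90% Wald interval with multiplier 1.64, and counts how often the lower bound lies above -20%.

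The output is labelled differently. Table 7.6:2 is titled "Summary of power estimates for primary efficacy endpoint with a sample size of 141". Table 7.6:3 enters 72% in a column for the primary endpoint's non-event rate, and its footnote names the Newcombe-Wilson interval. The text concludes that 141 patients give adequate power, at 82%.

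**The concern.** A rate for one component is used as the rate for a composite of three. Adding conditions can only remove successes, so the composite rate is at most 72%. Between 50% and 72%, a lower common rate means a larger binomial variance, and a fixed 20-point margin becomes harder to meet. If any child with complete resolution also has a recurrence or a VTE-related death, the stated 82% overstates the power of the planned test. Section 7.6 gives no composite rate, no recurrence rate and no statement of how recurrence overlaps with non-resolution, so a reader cannot tell by how much. The figure matters because it is the stated justification for 141 patients.

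**Working it through.** **Inputs.** n = 94 and 47; margin 20 points; multiplier 1.64; resolution rate 72% in both arms (all Protocol 7.6). Recurrence is taken from the randomised paediatric trial of reviparin versus UFH/VKA in Protocol 1.1.

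**Reproducing the plan's figure.** The rule was enumerated exactly: sum Bin(x; 94, p1) × Bin(y; 47, p2) over all (x, y) for which

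x/94 - y/47 - 1.64 × sqrt[(x/94)(1 - x/94)/94 + (y/47)(1 - y/47)/47] > -0.20.

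At 72% versus 72% this gives 81.8%; a 100,000-run simulation also gives 81.8%. The other rows of Table 7.6:2 come out at 95.2%, 63.3%, 32.3% and 4.7%, against the printed 95%, 63%, 33% and 5%. The arithmetic is therefore sound for the rate that was put in.

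**Which interval was used.** At 72%, Wald gives 81.8% with multiplier 1.64 and 71.3% with 1.96. Newcombe-Wilson gives 84.8% and 77.5%. Table 7.6:3 prints 82% and 71%, so its figures are Wald results despite the footnote.

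**Bounding recurrence.** Protocol 1.1 reports: "2/36 patients (5.6%) treated with reviparin-sodium had recurrent VTE or death compared to 4/40 patients (10.0%) receiving UFH/VKA". It also reports 1 and 4 deaths in those arms, none considered VTE-related, so the deaths do not themselves fail this trial's mortality component.

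- Reviparin: 2 patients with recurrence or death, 1 death, so 1 to 2 with recurrence.
- UFH/VKA: 4 patients with recurrence or death, 4 deaths, so 0 to 4 with recurrence.
- Pooled: 1/76 (1.3%) to 6/76 (7.9%).

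The lower bound assumes that all five deaths are counted in the recurrence-or-death figures.

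**Composite rate and power.** If recurrence e is independent of resolution, p = 0.72 × (1 - e); for example, 0.72 × (1 - 6/76) = 0.663. Both arms are set to p.

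| Recurrence e | Basis | p | Power, Wald | Power, Newcombe-Wilson |
|---|---|---|---|---|
| any, full overlap | every event in a non-resolver | 72.0% | 81.8% | 84.8% |
| 1.3% | 1/76 | 71.1% | 81.0% | 84.1% |
| 2.8% | 1/36, reviparin minimum | 70.0% | 80.1% | 83.4% |
| 5% | illustrative | 68.4% | 78.8% | 82.3% |
| 7.9% | 6/76 | 66.3% | 77.3% | 81.0% |

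**Hand check.** The standard error is sqrt[p(1 - p)(1/94 + 1/47)]: 8.02 points at 72% and 8.44 at 66.3%. The normal approximation, Φ(0.20/SE - 1.645), gives 80.2% and 76.5%, a fall of similar size.

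**Where 80% is lost.** Wald power reaches 80.0% at p = 69.9%. Under independence that is e = 1 - 0.699/0.72 = 2.9%.

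**The case against.** The strongest reply is overlap. Recurrent VTE in this endpoint includes contiguous and thrombus progression, and a progressing index clot will often be an unresolved one. If all events fall there, the composite rate is 72% and power is 82%. A reader might therefore infer too much by saying that the composite rate must be lower; the documents show only that it cannot be higher. Full overlap cannot be presumed either, because the endpoint also counts non-contiguous new thrombus, pulmonary embolism and asymptomatic events, which can occur after the index clot has resolved.

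A reader might also take the 10.0% in the UFH/VKA arm as a failure rate and arrive at 76% power (p = 64.8%). The documents do not support this. That 10.0% counts deaths not related to VTE, and reaching it as recurrence would require all four event patients in the worse arm to have recurred, with that arm then applied to both arms here. Placing every recurrence in a child with complete resolution at 6/76 also gives about 76% (p = 64.1%), but nothing in the documents supports that allocation.

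A third inference is that missing images, scored as failures, push the rate towards 60%. SAP 7.4 does score a child with no index assessment by Day 84 + 7 as not resolved. But it carries earlier assessments forward, exclusion criterion 13 removes families unwilling to repeat imaging, and no missing-image rate is given.

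The background trial is a loose proxy. It is small, closed early, and has a different observation window; the present trial starts after initial parenteral therapy but also counts asymptomatic events. SAP 7.4 expects recurrence to be low, without a figure.

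Finally, with the Newcombe-Wilson interval named under Table 7.6:3, power stays above 80% in every row above. That stands, but it does not rescue the printed figures, which are Wald, and power falls with the rate under either interval. It is also fair that the closing text of 7.6 states its assumption as a complete resolution rate; the mismatch lies in how the tables are labelled and used.

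**Conclusion.** The point holds as a mismatch between the rate used and the endpoint tested. The calculation itself is correct for its input. The 82% is the power for complete resolution alone. For the composite, under the protocol's Wald rule with equal arms, it is about 77-81% if recurrence lies in the 1.3-7.9% range and is independent of resolution, and up to 82% with full overlap. The shortfall is 0 to about 5 points. It rests on one small paediatric trial and on an overlap that the documents do not give. A reader might infer that the trial is underpowered or that 141 patients are too few. The documents do not support that: the loss is modest, and it is of the same order as the gap between the two intervals that 7.6 cites.

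**What to change.** In Protocol 7.6:

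- State the assumed rate for the composite as scored in SAP 7.4, with the recurrence rate and overlap assumption behind it.
- Rerun Tables 7.6:2 and 7.6:3 and the 82% sentence at that rate, which gives about 77-82% under the Wald rule.
- Use one named interval throughout, and make the Table 7.6:3 footnote agree with it.
- Keep the existing 72% rows if wanted, labelled 'complete resolution component only'.

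The cost is a wording change and a rerun of the existing simulation. The sample size does not need to change. The only downside is a slightly less favourable stated power.

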1. INTRODUCTION

1.1 MEDICAL BACKGROUND

In contrast to adults, venous thromboembolism (VTE) in children is a rare event with an overall annual incidence of approximately 0.07-0.14 events per 10,000 children ([R06-2301](#)). Nevertheless it represents a significant management dilemma that requires therapeutic intervention ([R06-2301](#), [R06-2150](#), [R07-2959](#)).

The most common etiologic factor for VTE in children is the presence of a central venous line (CVL) ([R06-2305](#), [R06-2150](#)). Immediate complications of VTE include death from pulmonary embolism (PE) and non-lethal PE. Long-term complications involve recurrent VTE, post-thrombotic syndrome (PTS), and bleeding associated with anticoagulation therapy ([R07-2959](#), [R07-2954](#), [R07-2962](#), [R06-2305](#)).

The recommendations on antithrombotic therapy in children are based on extrapolation of adult data from randomized controlled studies or on small randomized or non-controlled studies in children ([P98-11480](#), [R07-2940](#)). The current standard of care (SOC) for the treatment of VTE in children is unfractionated heparin (UFH) or low molecular weight heparin (LMWH) administered for generally 5 to 7 days followed by 3 to 6 months of LMWH or vitamin K antagonists (VKA) ([R07-2939](#)).

There are frequent challenges with the use of UFH and OAC in children ([P06-06652](#), [R07-2938](#), [R07-2956](#)). For UFH, these include variable pharmacokinetics, need for venous access for both administration and monitoring and heparin-induced thrombocytopenia. For VKA, problematic issues with dosing include the significant influences of age, diet, medications and underlying diseases, which result in a need for frequent monitoring ([R07-2964](#)). Low molecular weight heparin has several potential advantages in children over UFH / VKAs for the treatment of VTE, which has prompted it becoming the preferred product in children despite the lack of adequate and well-controlled clinical trials. However, the use of LMWH requires subcutaneous administration with a needle poke causing pain in the child and anxiety for the parent or guardian which may translate into non-compliance. These problems with conventional anticoagulation provide the rationale for investigations of novel anticoagulants.

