3.3.2 Inclusion criteria

- 1) Male or female subjects 0 to less than 18 years of age at the time of informed consent / assent.
- 2) Documented diagnosis of clinically stable VTE (e.g. DVT, PE, central line thrombosis, sinus vein thrombosis) per investigator judgment, initially treated (minimum of 5 to 7 days, but not longer than 21 days) with parenteral anticoagulation therapy, such as unfractionated heparin (UFH) or a low molecular weight heparin (LMWH)².
- 3) Anticipated treatment duration with anticoagulants for the VTE episode (under inclusion 2) for at least 3 month period, inclusive of the initial parenteral therapy.
- 4) Written informed consent provided by the patient's parent or legal guardian and assent provided by the patient (if applicable) at the time of ICF signature according to local regulations.

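### The statement that the 20% margin preserves at least 62% of the SOC effect is computed against no treatment, although every participant is anticoagulated before randomisation; the 62% floor fails if the lead-in-only resolution rate exceeds about 20%

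*Protocol*

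**What the plan says.** Protocol section 7.6 takes the control rate from published studies: "a Bayesian meta-analysis concluded a stable mean complete thrombus resolution rate of 72% using data from the 11 studies". For the other side of the contrast it concedes that "A complete thrombus resolution rate without treatment cannot be established from recent publications", and substitutes assumed values: "a wide range of plausible complete thrombus resolution rate without treatment (5% to 20%) have been considered". From these it concludes that "the proposed 20% non-inferiority margin can preserve at least 62% and up to 70% of the effect size under SOC treatment". Table 7.6:1 gives 70%, 68%, 65% and 62% for no-treatment rates of 5%, 10%, 15% and 20%.

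The entry rules describe a different starting point. Inclusion criterion 2 (section 3.3.2) requires patients to have been "initially treated (minimum of 5 to 7 days, but not longer than 21 days) with parenteral anticoagulation therapy". Section 3.3.1 expects this course in all participants, and section 3.1 places it in the screening period. The Flow Chart puts randomisation at Visit 2, after the course. The Flow Chart also lists the baseline VTE assessment at Visit 1, so a clot that clears during the lead-in can count as a success in either arm.

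Neither the protocol nor the SAP gives a resolution rate for the lead-in followed by no further treatment, and neither adjusts the preserved-effect calculation for the lead-in.

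**The concern.** A preserved-effect argument says how much of the control's benefit a drug could lose and still pass. That benefit has to be the one the randomised comparison can detect. Here both arms receive the lead-in and only the continuation phase is randomised, so a poor study drug can forfeit only what continuation SOC adds to the lead-in. Table 7.6:1 credits the margin with preserving part of an effect that includes whatever the lead-in achieved, which is common to both arms.

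Table 7.6:1 is the protocol's only quantitative support for the efficacy margin. If its reference rate is too low, a result that just meets the margin shows less retained benefit than the text states. Preserved effect mattered to regulators in this programme: section 11 records that the efficacy margin justification was updated on FDA advice, and that major bleeding ceased to be a co-primary endpoint after the FDA objected that its margin would not preserve the effect.

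**Working it through.** **Inputs.** SOC rate 72%, no-treatment rates 5% to 20% and margin 20 percentage points (section 7.6; the synopsis states the margin and the one-sided 0.05 level). Lead-in of minimum 5 to 7 days and at most 21 days (section 3.3.2). End-of-therapy assessment 84 days after Visit 2 (Flow Chart).

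**Step 1: reproduce the plan's figures.** Preserved share = 1 − margin / (SOC rate − reference rate).

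- Reference 5%: 1 − 0.20/0.67 = 70.1% (stated 70%)
- Reference 10%: 1 − 0.20/0.62 = 67.7% (stated 68%)
- Reference 15%: 1 − 0.20/0.57 = 64.9% (stated 65%)
- Reference 20%: 1 − 0.20/0.52 = 61.5% (stated 62%)

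The arithmetic is right. The question is what the reference row should represent.

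**Step 2: replace the reference by a lead-in-only rate.** The formula is unchanged. The share falls as the reference rises, so any net benefit of the lead-in lowers it. The stated minimum comes from the 20% column, so there is no slack: a lead-in-only rate above about 20% breaks it. No lead-in-only rate is documented, so the values below are assumptions.

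| Assumed lead-in-only rate | Effect at stake | Share preserved |
|---|---|---|
| 20% | 52 points | 61.5% |
| 30% | 42 points | 52.4% |
| 40% | 32 points | 37.5% |

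The share drops below one half once the reference exceeds 0.72 − 0.20/0.50 = 32%.

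**Step 3: link the lead-in to the protocol's own no-treatment range.** As an illustration only, suppose the SOC effect accrues evenly over the lead-in (L days) plus 84 days. Then lead-in-only rate = p + [L/(84 + L)] × (0.72 − p), where p is the no-treatment rate. For L = 21 the fraction is 21/105 = 0.20; for L = 5 it is 5/89 = 0.056.

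| No-treatment rate p | Stated share | 5-day lead-in | 21-day lead-in |
|---|---|---|---|
| 5% | 70% | 68.4% | 62.7% |
| 10% | 68% | 65.8% | 59.7% |
| 15% | 65% | 62.8% | 56.1% |
| 20% | 62% | 59.2% | 51.9% |

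Two cells in full, for L = 21. From p = 5% the reference is 0.05 + 0.20 × 0.67 = 18.4% and the share is 1 − 0.20/0.536 = 62.7%. From p = 20% the reference is 0.20 + 0.20 × 0.52 = 30.4% and the share is 1 − 0.20/0.416 = 51.9%.

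So under this illustration the floor holds in some cells and fails in others. The 20% column falls below it for either lead-in length.

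**Step 4: what is not affected.** Re-simulating the protocol's confidence-interval formula with 94 and 47 patients at 72% in both arms gives 81.8%, against the stated 82%. The reference rate does not enter the power calculation.

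**The case against.** The strongest defence is that Table 7.6:1 is coherent as labelled. Section 1.1 describes SOC as initial heparin followed by continuation, the planned 3 months include the initial course, and the table compares that whole course with nothing. Section 7.6 states openly that the no-treatment rate is unknown and calls its values assumptions. The case for the drug also draws on adult trials. All of this is true, but disclosing the uncertainty does not make full course versus nothing the contrast that randomisation tests.

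A second defence is that stopping after the lead-in would invite recurrence or progression, which count as failures on the composite endpoint. Section 2.3 says the thrombotic risk is highest in the first 30 days. Clots resolved during the lead-in would then not carry over one for one. This shrinks the net lead-in benefit, but it does not restore the floor unless it removes that benefit entirely.

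Three stronger readings are tempting, and the documents do not support them.

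- *The true reference rate lies above 20%.* No lead-in-only rate is given. In the illustration above, a 5% no-treatment rate with a 21-day lead-in gives 18.4%, inside the table's range.
- *Sections 1.1 and 7.6 contradict each other on central lines.* Section 1.1 calls a central line the commonest cause of VTE in children generally. Section 7.6 says that "the number of central line thrombosis in this trial is expected to be low overall", because such cases cluster below about 2 years of age and stratum 3 is about 15 patients. The two statements concern different populations. More central-line cases could also raise the SOC rate, not only the reference.
- *The SOC rate should be lowered as well, for example to 68%.* In Table 7.6:2 the SOC rate is 72% throughout, and 68% appears only as a dabigatran scenario.

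**Conclusion.** The point holds. A preserved share of at least 62% is not a property of this design, because it is calculated against a reference that no participant represents. For any given no-treatment rate the share is no higher than stated, and it is lower if the lead-in resolves any clots.

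The direction rests on one assumption: that the lead-in followed by nothing gives a net resolution rate at least as high as no treatment. This fits the protocol's premise that anticoagulation lifts resolution from 5% to 20% up to 72%. The size cannot be established from the documents; the shares at 30% and 40% show sensitivity and are not estimates.

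A reader might infer that the margin is invalid or the trial underpowered. Neither follows: the flaw lies in the stated justification of the margin and leaves the hypothesis test as it is.

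**What to change.** In Table 7.6:1, relabel the reference row as complete resolution with the initial parenteral course only. Keep the 5% to 20% columns and extend them upward, for example to 30% and 40%, all labelled as assumptions. Replace the stated minimum of 62% with the range that results: 70% at a reference of 5%, 61.5% at 20%, 52% at 30% and 37.5% at 40%.

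In the report, show the share preserved at the observed 90% bound across the same reference rates, as 1 − U/(0.72 − reference), where U is the upper bound for the SOC minus dabigatran difference. Giving it across the range avoids relying on one unknown value.

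The cost is wording in the protocol and one small table in the report. Margin, test, sample size and the 82% power stay as they are. The downside for the sponsor is a less favourable stated preserved share.
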